### 7.1.2 QTc stopping criteria

If the participant reports an AE which could be due to a cardiac condition, an ECG should be performed.

A participant with corrected QT interval (QTc) $>500$  msec OR Uncorrected QT $>600$  msec based on the average of triplicate ECG readings will be withdrawn from study medication.

Any new clinically relevant finding should be reported as an AE.

## 7.2 Participant discontinuation/withdrawal from the study

Participants or the participant's legal representatives are free to withdraw the participant from the study at any time, without prejudice to their continued care.

A participant may withdraw from the study at any time at his/her own request or at the study participant's legal representative's request, or may be withdrawn at any time at the discretion of the Investigator for safety, behavioral, compliance, or administrative reasons.

If a participant withdraws consent for disclosure of future information, the Sponsor may retain and continue to use any data collected before such a withdrawal of consent.

If a participant withdraws from the study, he/she may request destruction of any samples taken and not tested, and the Investigator must document this in the site study records.

See the Schedule of Activities (Table 1-1) for data to be collected at the time of study discontinuation and follow up and for any further evaluations that need to be completed.

Participants must be withdrawn from this study if any of the following events occur:

- Participant experiences intolerable AEs, including clinically relevant abnormal laboratory findings that, in the opinion of the Investigator, preclude further participation in the study.
- The Sponsor or a regulatory agency requests withdrawal of the participant.
- Participant is unwilling or unable to continue or legal representative is unwilling or unable to allow the participant to continue in the study.
- Investigator decides that withdrawal from further participation would be in the participant's best interest.

Participants should be withdrawn from the study if any of the following events occur:

1. Participant develops an illness that would interfere with his/her continued participation
2. Participant and/or legal representative is noncompliant with study procedures or medication, in the opinion of the Investigator
3. Participant takes prohibited concomitant medications as defined in this protocol (Section 6.5.2)
4. Participant withdraws his/her consent
5. Any clinically relevant change in medical or psychiatric condition (if, in the opinion of the Investigator, the condition warrants discontinuation from the study)

Study Participants discontinuing LCM for any reason should taper off medication as described in Section 4.1. Whenever possible, these cases should be discussed with the Medical Monitor prior to withdrawing the participant from the study

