### Early Termination Visit with tapering of LCM

Study participants who discontinue prematurely from EP0151 and who will not continue further treatment with LCM should gradually taper LCM. These study participants will perform an Early Termination Visit followed by the visits required for the End of Study Period. Study participants should be tapered off LCM at the recommended decrements (Table 6-2). The Taper Period is up to 4 weeks; a slower taper or faster taper is permitted, if medically necessary; however, the maximum duration of tapering should not exceed 6 weeks. All study participants who taper off LCM will attend a Final Visit 30 days after the final dose of LCM. In the case of LCM withdrawal and taper, the Investigator is allowed to add any other antiepileptic drugs (AEDs) during the End of Study Period, following the Investigator's medical judgment.

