### Termination Visit

Study participants who remain in the Treatment Period and either reach 6 years of age or who participate in a region where marketing application approval is achieved for pediatric patients  $<4$  years of age and LCM oral solution is available (whichever is earliest) will have met the conditions for completing the study. A Termination Visit will be performed for these study participants at the time of the next scheduled visit. Study participants who reach the end of the study and choose to continue treatment with LCM may be immediately prescribed LCM. The Termination Visit will be the last study visit completed for study participants who continue treatment with prescribed LCM. Study participants who choose not to continue with LCM treatment and who are taking a dose of LCM 3mg/kg/day or higher will enter an End of Study Period following completion of the Termination Visit, and will gradually taper from LCM treatment during the Taper Period; a Final Visit will be conducted 30 days after the final dose of LCM.

In situations where provision of LCM oral solution in certain participants  $>6$  years of age (eg, developmental delay, need for more precise dosing as afforded by oral solution formulation, etc.) who may need a longer period of treatment with LCM oral solution, the situation will be

assessed for approval by UCB on a case-by-case basis following discussions with the participant's physician.

The maximum total duration of the study will be approximately 213 weeks, including an approximate 205-week Treatment Period and up to an 8 week End of Study Period (4-week Taper Period and 30-day Safety Follow-up Period). The end of the study is defined as the date of the last visit of the last study participant in the study.

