**Table 6-1: Summary of treatments administered**

ARM Name	
Intervention name	Lacosamide
Type	Drug
Dose formulation	Oral solution
Unit dose strength(s)	LCM 10mg/mL
Dosage level(s)	Minimum dose of 2mg/kg/day to maximum dose of 12mg/kg/day or 600mg/day, whichever is lower, administered BID in the morning and evening.
Route of administration	Oral use
Use	Active open-label
IMP and NIMP	IMP
Sourcing	Provided by UCB
Packaging and labeling	Clinical drug supplies will be labeled in accordance with the current ICH guidelines on GCP and GMP and will include any locally required statements. If necessary, labels will be translated into the local language. Primary packaging: bottles with child-resistant closure
Current/former name(s) or alias(es)	Not applicable

BID=twice per day; GCP=Good Clinical Practice; GMP=Good Manufacturing Practice; ICH=International Council for Harmonisation; IMP=investigational medicinal product; LCM=lacosamide; NIMP=non-IMP

Study participants will receive LCM oral solution administered BID from a minimum dose of 2mg/kg/day to a maximum dose of 12mg/kg/day or 600mg/day, whichever is lower, based on optimization of seizure control and tolerability in the judgement of the Investigator.

The Investigator may maintain the LCM dose administered to the study participant in the previous study, decrease the dose to a minimum dose of LCM 2mg/kg/day, or increase the dose to a maximum dose of LCM 12mg/kg/day or 600mg/day, whichever is lower. An IXRS will be used and should be called any time there is a dose increase or dose reduction.

Study participants who are taking a dose of 3mg/kg/day or higher and who either withdraw during the study or complete the study and do not continue treatment with LCM should taper off LCM.

It is recommended that the dose be tapered gradually in weekly decrements according to [Table 6-2](#). A slower taper is permitted, if medically necessary, but should not exceed 6 weeks. In case of an emergency, a faster taper is permitted, after discussion with the Medical Monitor whenever possible.

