**Table 6-2: Lacosamide doses for Taper Period**

LCM dose achieved	LCM doses for Taper Period			
	Week 1	Week 2	Week 3	Week 4
11-12mg/kg/day	9mg/kg/day	6mg/kg/day	4mg/kg/day	2mg/kg/day
9-10mg/kg/day	8mg/kg/day	6mg/kg/day	4mg/kg/day	2mg/kg/day
7-8mg/kg/day	6mg/kg/day	4mg/kg/day	2mg/kg/day	2mg/kg/day
5-6mg/kg/day	4mg/kg/day	2mg/kg/day	2mg/kg/day	----
3-4mg/kg/day	2mg/kg/day	2mg/kg/day	----	----

LCM=lacosamide

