### 7.1 Discontinuation of study medication

#### 7.1.1 Liver chemistry stopping criteria

Discontinuation of study treatment for abnormal liver function should be considered by the Investigator when a participant meets one of the conditions outlined in [Figure 7-1](#) or [Figure 7-2](#) or if the Investigator believes that it is in best interest of the participant.

Study medication will be discontinued immediately and permanently for a study participant if liver chemistry stopping criteria are met.

[figure not shown]

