**Figure 7-1: Liver chemistry stopping criteria and increased monitoring algorithm**

ALT=alanine aminotransferase; AST=aspartate aminotransferase; INR=international normalized ratio; SAE=serious adverse event; ULN=upper limit of normal

Note: Algorithm for continued therapy with increased liver chemistry monitoring can be found in [Figure 7-2](#).

**Figure 7-2: Liver chemistry increased monitoring algorithm with continued study intervention for participants with ALT  $\geq 3$ xULN but  $< 8$ xULN**

ALT=alanine aminotransferase; AST= aspartate aminotransferase; bili=bilirubin; INR=international normalized ratio; SAE=serious adverse event; ULN=upper limit of normal

Specific assessments and follow-up actions for potential drug-induced liver injury are provided in Appendix 6 (Section 10.6).

Study participants with potential drug-induced liver injury (PDILI) must be assessed to determine if study medication must be immediately and permanently discontinued. In addition, all concomitant medications and herbal supplements that are not medically necessary should also be discontinued.

The PDILI criteria below require immediate and permanent discontinuation of study medication:

- Participants with either of the following:
  - Alanine aminotransferase (ALT) or aspartate aminotransferase (AST)  $\geq 5$ x upper limit of normal (ULN)
  - ALT or AST  $\geq 3$ xULN and coexisting total bilirubin  $\geq 2$ xULN

The PDILI criterion below requires immediate discontinuation of study medication:

- Participants with ALT or AST  $\geq 3$ xULN who exhibit temporally associated symptoms of hepatitis or hypersensitivity. Hepatitis symptoms include fatigue, nausea, vomiting, right

upper quadrant pain or tenderness. Hypersensitivity symptoms include fever (without clear alternative cause), rash, or eosinophilia (ie, >5%).

The PDILI criterion below allows for participants to continue on study medication at the discretion of the Investigator:

- Participants with ALT or AST  $\geq 3 \times \text{ULN}$  (and  $\geq 2 \times \text{Baseline}$ ), and  $< 5 \times \text{ULN}$ , total bilirubin  $< 2 \times \text{ULN}$ , and no eosinophilia (ie,  $\leq 5\%$ ), with no fever, rash, or symptoms of hepatitis (eg, fatigue, nausea, vomiting, right upper quadrant pain or tenderness).

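### Section 7.2 asks everyone stopping lacosamide to taper without excepting the immediate liver stops, and those who stop on 2 to <3 mg/kg/day have no clearly assigned contact in the 30-day TEAE window

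*Protocol*

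**What the plan says.** **Taper and liver stops.** Protocol Section 7.2 closes its withdrawal lists with: "Study Participants discontinuing LCM for any reason should taper off medication as described in Section 4.1". Section 7.1.1 says: "Study medication will be discontinued immediately and permanently for a study participant if liver chemistry stopping criteria are met". The criteria for potential drug-induced liver injury (PDILI) in the same section repeat this ("The PDILI criteria below require immediate and permanent discontinuation of study medication") and add an immediate stop for symptomatic cases. Table 10-1 in Section 10.6 also calls for immediate discontinuation. On taper length, Section 4.1 permits a slower or faster taper if medically necessary, but "the maximum duration of tapering should not exceed 6 weeks". Section 6.1 adds: "In case of an emergency, a faster taper is permitted, after discussion with the Medical Monitor whenever possible".

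**Who is followed after the last dose.** Section 6.1 asks for a taper from "Study participants who are taking a dose of 3mg/kg/day or higher and who either withdraw during the study or complete the study" without continuing LCM. Under the Termination Visit heading of Section 4.1, completers who do not continue LCM and "who are taking a dose of LCM 3mg/kg/day or higher will enter an End of Study Period" then have a Final Visit 30 days after the last dose. The synopsis (Section 1.1) and SAP Section 1.2 carry the same threshold, and apply it after either the Termination or the Early Termination Visit. Footnote d to Table 1-1 links the End of Study Period to needing a taper. Footnote e gives the Final Visit with no dose condition. The lowest permitted dose is 2 mg/kg/day.

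**Event window.** Protocol Section 9.3.1 and SAP Section 5.3.1 count events up to 30 days after the final EP0151 dose as treatment-emergent. TEAEs are a primary endpoint.

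**The concern.** The two halves share a cause: the stopping rules, the taper rules and the follow-up rules were not fully cross-referenced.

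A child who meets a liver criterion falls under two instructions. One says stop now. The other says anyone stopping should taper, and the text it points to offers a faster taper but never an omitted one. In a child with epilepsy there is a real clinical pull towards tapering. The investigator has to infer the exception, when the protocol could simply state it.

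A child who finishes the study on 2 to <3 mg/kg/day and stops LCM needs no taper under Section 6.1. The paragraphs that lead to the Final Visit then do not clearly reach that child. Section 8.3.1 collects adverse events at the time points in Table 1-1. Without an assigned time point after the Termination Visit, new non-serious events after stopping may never be asked about, although the analysis definition counts them.

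**Working it through.** No planned figure is at issue and the documents state none, so the check is mainly a comparison of texts.

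**A. Is there an exception to the taper?**
1. Section 7.2 covers every reason for discontinuing LCM and refers to Section 4.1.
2. Section 4.1 allows a faster taper if medically necessary and sets a maximum of 6 weeks but no minimum. Section 6.1 allows a faster taper in an emergency. Neither says the taper may be omitted.
3. Section 7.1.1 and Table 10-1 require an immediate stop and do not mention tapering.
4. Figures 7-1 and 7-2 are not reproduced in the text available. I assume they contain no taper exemption.

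The written conflict stands. To see its size, apply the recommended schedule ("Table 6-2: Lacosamide doses for Taper Period") at 7 days per step:

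- 11-12 mg/kg/day: (9 + 6 + 4 + 2) × 7 = 147 mg/kg over 28 days
- 9-10 mg/kg/day: (8 + 6 + 4 + 2) × 7 = 140 mg/kg over 28 days
- 7-8 mg/kg/day: (6 + 4 + 2 + 2) × 7 = 98 mg/kg over 28 days
- 5-6 mg/kg/day: (4 + 2 + 2) × 7 = 56 mg/kg over 21 days
- 3-4 mg/kg/day: (2 + 2) × 7 = 28 mg/kg over 14 days

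Under Section 7.1.1 the figure is zero. These totals are what the recommended schedule would deliver. Because no minimum taper is set, even a literal reading of Section 7.2 does not compel them.

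**B. Who is assigned a contact after the last dose?**
- *Completers stopping on 3 mg/kg/day or higher:* End of Study Period and Final Visit (Sections 1.1 and 4.1). Clear.
- *Completers continuing on prescribed LCM:* the Termination Visit is their last visit (Sections 1.1 and 4.1). Clear.
- *Completers stopping on 2 to <3 mg/kg/day:* not reached by Sections 1.1 or 4.1, nor by the taper link in footnote d. Reached by footnote e only if it is read as applying to everyone. Unclear.
- *Early terminators stopping on 2 to <3 mg/kg/day:* the early-termination paragraph of Section 4.1 has no threshold and sends them to the End of Study visits, while the synopsis applies the threshold. Mixed, but better covered than completers.

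SAP Section 5.1.2.1.3 names the Final Visit as the only scheduled visit in safety follow-up, so nothing else fills the gap.

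If footnote e does not apply to such a completer, and the last dose falls at the Termination Visit, the share of the TEAE window without an assigned contact is 30 / (treatment days + 30):

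- 205 weeks (the approximate maximum): 30 / (1,435 + 30) = 2.0%
- 104 weeks (assumed): 30 / (728 + 30) = 4.0%
- 26 weeks (assumed, one visit interval): 30 / (182 + 30) = 14.2%

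These are shares of time, not of events.

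**The case against.** **On the taper.** The best defence is that a specific rule using *will* overrides a general sentence using *should*. Section 7.1 governs stopping medication, whereas the Section 7.2 sentence sits among rules on leaving the study. Section 10.6 says children with potential liver injury should not be withdrawn until the work-up is complete. All of this stands, and I expect most investigators would stop the drug. A reader might infer that the protocol orders two to four weeks of further dosing in a child with a liver signal. The documents do not support that: the decrements are recommended, a faster taper has no minimum length, and the immediate stop is stated repeatedly. What remains is that the exception has to be inferred.

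**On follow-up.** It can be argued that if Section 7.2 is taken literally, low-dose stoppers also taper, and Section 4.1 gives everyone who tapers a Final Visit. This fails because the taper table has no row below 3 mg/kg/day and Section 6.1 sets the same threshold. The argument from footnote e is stronger. It states a Final Visit without a dose condition, and the last sentence of footnote d can be read the same way. A reader might infer that 30 days are plainly uncovered for these children. The documents show only that coverage is not clearly assigned.

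**On importance.** Section 8.3.1 collects serious events for 30 days after each participant's end of study. Section 8.2.3 has clinically significant laboratory abnormalities repeated if they arise within 30 days of the last dose. Section 10.3 follows events already reported. None of these provides a contact to detect new non-serious events, but they limit what can be lost. Completers who move to prescribed LCM also have no visit in the 30 days after their final EP0151 dose. For them the protocol says plainly that the study ends at the Termination Visit, and they have not stopped the drug.

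**Conclusion.** Both halves hold, and both are minor.

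(A) The wording of Section 7.2 conflicts with the immediate liver stops. The liver rule probably prevails. The totals of 14 to 28 days and 28 to 147 mg/kg describe the recommended schedule and are neither required nor expected exposure.

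(B) Participants who permanently stop LCM on 2 to <3 mg/kg/day, mainly completers, have no clearly assigned contact after the Termination Visit. Non-serious TEAEs in the last 30 days of the window may be missed. The documents do not give the number of such children. It is probably small, since each must be in that dose band and stop LCM, so the effect on TEAE incidence cannot be sized. The study is descriptive with no hypothesis test, and no conclusion is shown to change.

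The verdict assumes that the liver figures add no taper exemption and that footnote e is not clearly meant to override the dose threshold.

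**What to change.** 1. In Section 7.2, add to the taper sentence: *except where immediate discontinuation is required under Section 7.1.1 or 10.6*.
2. In Sections 1.1 and 4.1 and in footnotes d and e to Table 1-1, require the existing 30-day Final Visit, or a telephone adverse-event contact, for everyone who permanently stops LCM, whatever the dose and whether or not they taper. Exclude those continuing on prescribed LCM.
3. Align the design description in SAP Section 1.2, which repeats the 3 mg/kg/day threshold. The analysis definitions can stay: SAP Section 5.1.2.1.3 already runs the End of Study Period to the Final Visit or last contact.

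The cost is a protocol amendment with ethics committee approval, a small edit to the SAP text, and one extra visit or call for a few children.

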**Table 10-1: Phase 3-4 liver chemistry stopping criteria and follow-up assessments**

Liver Chemistry Stopping Criteria	
ALT-absolute	ALT≥8xULN
ALT increase	ALT≥5xULN but <8xULN persists for ≥2 weeks ALT≥3xULN but <5xULN persists for ≥4 weeks
Bilirubina,b	ALT≥3xULN and bilirubin ≥2xULN (>35% direct bilirubin)
INRb	ALT≥3xULN and INR>1.5, if INR measured
Cannot monitor	ALT≥5xULN but <8xULN and cannot be monitored weekly for ≥2 weeks ALT≥3xULN but <5xULN and cannot be monitored weekly for ≥4 weeks
Symptomatic	ALT≥3xULN associated with symptoms (new or worsening) believed to be related to liver injury or hypersensitivity
Suggested Actions and Follow up Assessments	
Actions	

• Immediately discontinue study medication

• Report the event to UCB within 24 hours

• Complete the Liver Event eCRF, and complete an SAE data collection tool if the event also met the criteria for an SAEb

	
Follow-up Assessments	

• Viral hepatitis serologyd

• Obtain INR and recheck with each liver chemistry assessment until the transaminases values show downward trend

	

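### Section 7.2 asks everyone stopping lacosamide to taper, with no visible exception for the liver criteria that Section 7.1.1 says require an immediate stop

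*Protocol*

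**What the plan says.** **Taper side**

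- Protocol Section 7.2, in its closing paragraph: "Study Participants discontinuing LCM for any reason should taper off medication as described in Section 4.1".
- Protocol Section 4.1, on early termination with tapering, covers participants who leave the study early and will not continue lacosamide (LCM): "The Taper Period is up to 4 weeks; a slower taper or faster taper is permitted, if medically necessary". The maximum is 6 weeks.
- Protocol Section 6.1 applies the taper from 3 mg/kg/day upward. "It is recommended that the dose be tapered gradually in weekly decrements according to" Table 6-2, headed "Lacosamide doses for Taper Period". In an emergency a faster taper is allowed, after discussion with the Medical Monitor whenever possible.

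**Liver side**

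- Protocol Section 7.1.1 opens softly: the Investigator should consider discontinuation. It then says: "Study medication will be discontinued immediately and permanently for a study participant if liver chemistry stopping criteria are met".
- Later in the same section: "The PDILI criteria below require immediate and permanent discontinuation of study medication". The criteria listed are ALT or AST at least 5 times the upper limit of normal (ULN), or at least 3 times ULN with total bilirubin at least 2 times ULN. A separate criterion, ALT or AST at least 3 times ULN with symptoms of hepatitis or hypersensitivity, requires an immediate stop.
- Table 10-1 tells the site to immediately "discontinue study medication" and to report to the sponsor within 24 hours. Both appear under a heading that calls the actions suggested.
- Section 10.6 keeps liver cases in the study until investigation and monitoring are complete.

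The SAP (Sections 1.2 and 5.1.2.1.3) repeats the taper design and adds no exemption.

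**The concern.** The same child can fall under both instructions. Section 7.2 speaks of stopping the drug, whatever the reason, and Section 7.1.1 describes one such reason. Taper doses are study medication: footnote n of Table 1-1 has LCM dispensed at the Termination or Early Termination Visit only when a taper is needed. Stopping at once and tapering are therefore mutually exclusive.

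What is at stake is participant safety. A site that applies Section 7.2 literally keeps giving the suspected drug to a young child whose liver tests have reached a stopping level. A site that applies Section 7.1.1 gives nothing more. No visible text says which sentence prevails.

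There is a minor effect on the analysis. The last-dose date sets exposure duration (SAP Section 5.1.2.3) and the 30-day window for treatment-emergent events (SAP Section 5.3.1), so two sites handling the same event differently would produce different derived values.

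**Working it through.** The plan states no figure on this point, so there is none to reproduce. The check has two parts.

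**1. Is there an exemption?** I compared Protocol Sections 4.1, 6.1, 7.1.1, 7.1.2, 7.2 and 10.6, Tables 1-1, 6-2 and 10-1, and the SAP's design and period definitions.

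- By dose: yes. Section 6.1 starts the taper at 3 mg/kg/day, and Table 6-2 has no lower row.
- By speed: in part. Sections 4.1 and 6.1 allow a faster taper and set no minimum length. Neither mentions omitting it or names the liver criteria.
- By reason for stopping: none in the visible text. Figures 7-1 and 7-2 are not shown.

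**2. How far apart are the two instructions?** Inputs are the weekly doses in Table 6-2.

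- Further dose = (sum of weekly daily doses) × 7.
- Week 1 share = Week 1 dose ÷ previous dose, over the range of the row.
- Dose by 24 and 72 hours = Week 1 daily dose × 1 and × 3. These are the times Table 10-1 sets for repeat liver tests: within 24 hours for the bilirubin or INR criteria, 24 to 72 hours for the others.

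| Dose before stop (mg/kg/day) | Further dose (mg/kg) | Days | Week 1 share | By 24 h (mg/kg) | By 72 h (mg/kg) |
|---|---|---|---|---|---|
| 11–12 | (9+6+4+2)×7 = 147 | 28 | 9/12 to 9/11 = 75–82% | 9 | 27 |
| 9–10 | (8+6+4+2)×7 = 140 | 28 | 8/10 to 8/9 = 80–89% | 8 | 24 |
| 7–8 | (6+4+2+2)×7 = 98 | 28 | 6/8 to 6/7 = 75–86% | 6 | 18 |
| 5–6 | (4+2+2)×7 = 56 | 21 | 4/6 to 4/5 = 67–80% | 4 | 12 |
| 3–4 | (2+2)×7 = 28 | 14 | 2/4 to 2/3 = 50–67% | 2 | 6 |
| Any, immediate stop | 0 | 0 | 0% | 0 | 0 |

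The totals are what a completed standard schedule would deliver. A faster taper, or one cut short by the sponsor, gives less. For the same child, the last-dose date would move by 14 to 28 days, and exposure duration and the end of the event window would move with it.

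**The case against.** The strongest reply is that the protocol, read as a whole, already lets the liver rule win.

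- **Scope.** The taper sentence sits in the section on leaving the study, and the sentence after it concerns discussion before withdrawal. Sections 4.1 and 6.1 also speak of participants who leave or complete the study, whereas liver cases stay in it. This narrows the conflict. It does not remove it, because the Section 7.2 sentence itself is about stopping LCM and allows for any reason.
- **Strength.** A specific, firm rule faces a general *should* that points to a recommended schedule. This stands, and most investigators would probably act on it.
- **Oversight.** A stopping event is reported within 24 hours. Section 8 sends immediate safety concerns to the sponsor at once, Section 10.6 requires an agreed monitoring plan when ALT exceeds 5 times ULN, and Section 7.2 asks for Medical Monitor discussion whenever possible. This stands too: a full taper after a liver stop is unlikely. The first day or so of dosing is less protected.
- **Unseen figures.** Figure 7-1 is the stopping algorithm and might contain a note on tapering. Even then, the unqualified sentence in Section 7.2 would need correcting.

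A reader might go further and infer three things that the documents do not support:

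- **That the protocol obliges sites to continue dosing for weeks.** It does not: the taper is recommended and may be faster.
- **That Table 10-1 is a second firm requirement.** Its action is listed as suggested. The firm text is in Section 7.1.1.
- **That a child stopped without a taper has no Final Visit and no route to another antiepileptic drug (AED).** Section 4.1 does tie the visit to tapering ("All study participants who taper off LCM will attend a Final Visit 30 days after the final dose of LCM"), but footnote e of Table 1-1 also states the 30-day visit without that condition. Section 6.5.1 permits new AEDs subject to conditions, and Section 6.5.3 says necessary therapy must not be refused and allows any rescue medication.

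**Conclusion.** The two instructions conflict in the visible text for any participant on 3 mg/kg/day or more who meets a liver criterion requiring an immediate stop. The practical risk is small, because the liver rule is more specific and more firmly worded and the sponsor is involved within a day. It still should be corrected: this is a safety instruction for young children, and sites should not have to work out which sentence governs.

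The size, if Section 7.2 is followed literally and Table 6-2 is completed, is 28 to 147 mg/kg of further LCM over 14 to 28 days, against 0. In Week 1 the child would still receive 50% to 89% of the previous dose. These figures assume the standard schedule with no intervention by the sponsor. No number of affected children can be given without a liver-event rate. Sample size and error rates are untouched, since the study tests no hypothesis. The conclusion also rests on Figures 7-1 and 7-2 containing no exemption, which could not be verified.

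**What to change.** In Section 7.2, replace the taper sentence with:

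> Participants discontinuing LCM should taper as described in Section 4.1, except when a liver criterion in Section 7.1.1 requires immediate discontinuation; in that case no taper doses are given and another AED may be started at once in the Investigator's judgment.

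Add a cross-reference to this exception in Sections 4.1 and 6.1. The AED wording is useful because Section 6.5.1 reserves new AEDs for participants with an inadequate response to a maximum tolerated LCM dose, which does not describe a liver stop.

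Do not add rules on the timing of the Early Termination and Final Visits in the same edit. Under Table 10-1, liver monitoring runs until the abnormalities resolve, stabilize or return to baseline, which may take more than 30 days. Holding the Early Termination Visit until monitoring ends, with the Final Visit fixed at 30 days after the last dose, could reverse the visit order in footnote e of Table 1-1 and in SAP Sections 5.1.2.1.3 and 5.1.2.1.4.

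The clause does not settle which threshold applies: Section 7.1.1 stops at ALT 5 times ULN, while Table 10-2 lets some participants from 5 to below 8 times ULN continue. That needs its own correction.

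The cost is one sentence and two cross-references in a protocol amendment, with no new procedures or data. The downside is the loss of gradual withdrawal, which the immediate-stop rule already implies.
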